CLINICAL STUDY PROTOCOL

R&D registration number = **14SG04**

Title

Correlation of nasopharyngeal and lower oesophageal temperatures in children ventilated with an endotracheal tube with leak

Purpose

Non-commercial study to find agreement between methods

Study investigators

[name] – Locum Consultant, Great Ormond Street Hospital Department of Anaesthesia

[contact]

Email: [contact]

-

[name] – Research Fellow, Great Ormond Street Hospital Department of Anaesthesia

[contact]

Email: [contact]

Background

During surgery under general anaesthesia a patient tends to cool down due to radiation, convection, evaporation and conduction (1). Under anaesthesia a patient loses their ability to regulate their own body temperature and solely relies on the anaesthetist to control their temperature with warming and cooling devices. Perioperative hypothermia is known to cause multiple complications such as surgical wound infection, coagulopathy, prolonged drug metabolism, shivering and increased oxygen consumption, all of which can affect patient outcome (2). However, hyperthermia in children also comes with risks such as febrile seizures or increased metabolic activity, so it is important to find a balance of maintaining normothermia (36.5°C to 37.5°C) accurately. In order to achieve this, temperature is routinely monitored under anaesthesia. NICE guidelines (3) recommend that temperature be monitored at least every 30 minutes. Continuous temperature monitoring devices such as those based on a thermistor design are commonly placed by anaesthetists, and indeed anaesthetic machines are routinely equipped to be compatible with this technology. NICE also recommends that when using a device to measure temperature, anaesthetists should be aware of adjustments that may need to be made to estimate core temperature from recorded temperature. Different sites of temperature measurement correlate to varying degrees with actual core temperature. Measuring core temperature in the patient's heart is the gold standard upon which to base decisions regarding temperature management, but measurement is invasive with a risk of complications (4) and is thus inappropriate in the vast majority of cases. Therefore alternative sites are generally used as surrogates of core temperature and it is important to identify a site that precisely reflects temperature of the core.

Oesophageal temperature accurately reflects core temperature (5) when a probe is positioned in the lower oesophagus (excluding open heart or lung surgery). However, the position of this probe must accurately be in the lower third of the oesophagus, lest a higher location is influenced by the cooler tracheal temperature (6-9). Compared to an adult, the short distance between the stomach, lower and middle oesophagus in a child makes reliable placement challenging. In order to achieve the precise placement of oesophageal temperature probes in adults and children, some formulas (10, 11) have been devised with varying success but none is perfect and accurate oesophageal temperature probe placement remains elusive, limiting the usefulness of the site.

The nasopharynx receives a good blood supply via the external carotid artery and therefore could correlate well with core temperature. The nasopharyngeal temperature probe confers the advantage of simplicity of placement compared to its oesophageal counterpart. The value of nasopharyngeal temperature's correlation with that of the core is generally regarded as accurate (12-14) in adults. In children undergoing anaesthesia often uncuffed endotracheal tubes are utilized, as historically in paediatric anaesthesia there have been concerns about subglottic stenosis and postoperative stridor (15) but to date there is no evidence that newer Microcuff® tubes are any less safe in children than uncuffed tubes (19). The use of uncuffed tubes is in direct contrast to adults, in whom cuffed endotracheal tubes are placed by anaesthetists. In the paediatric population very little evidence exists, although in small, poor quality trials findings are favourable for nasopharyngeal temperature comparisons to core (16). When a patient is ventilated during general anaesthesia, a humidity and moisture exchange filter (HMEF) assists in warming inspired gases administered from an anaesthetic machine, but does so incompletely (not achieving body temperature). With an uncuffed

endotracheal tube an escape of ventilated gases from the trachea upwards towards the mouth and nose occurs via the nasopharynx. With a temperature that is lower than body temperature, even at low flows, (17) these gases could possibly have a cooling effect on temperature in the nasopharynx (18). The question remains, thus, whether or not nasopharyngeal temperature is influenced by the cooling effects of these escaped gases or not.

Study objectives

This study will seek to find an agreement of methods (lower oesophageal and nasopharyngeal sites) to measure temperature in children undergoing general anaesthesia with an endotracheal tube that has a leak. This is an important question to answer because it is not known whether or not oesophageal and nasopharyngeal temperatures correlate in children ventilated with an uncuffed endotracheal tube, and would allow clinicians to confidently use the more feasible nasopharyngeal temperature probes if this were the case.

Study Design

Prospective, unblinded, cross-sectional (observational) agreement study

Approval will be obtained from the Research Ethics Committee

Written parental informed consent will be obtained prior to investigation. Parents will be informed of their right to withdraw at any stage of the trial without compromising their clinical care.

Inclusion criteria

Age: 8 months to 7 years

Patient requires general anaesthesia with endotracheal intubation for a procedure assisted by radiography (e.g. line insertion, line change)

Patient requires chest radiograph for procedure

Expected anaesthetic time more than 30 minutes

Exclusion criteria

No written parental written consent

Known oesophageal pathology (e.g. tracheo-oesophageal fistula, oesophageal strictures, oesophageal varices, oesophageal atresia)

Known base of skull or midface fractures

Previous gastric bypass surgery or nasal surgery

Known coagulopathy

Previous alkaline ingestion

High aspiration risk

Significant respiratory co-morbidity requiring anticipated peak airway pressures $> 25 \text{ cmH}_2\text{O}$

ASA 4 – 5

Tracheostomy in situ

Severe sepsis or septic shock or other other condition (such as bronchopulmonary fistula) that precludes use of tidal volume ventilation over 7 ml/kg

Known airway abnormalities (e.g. subglottic stenosis) that preclude placement of a MicroCuff® endotracheal tube

Oesophageal or nasopharyngeal probe contraindicated for reasons related to surgery / procedure

Feasibility of study/ number of patients

Statistical advice and analysis has been sought from the Great Ormond Street Hospital/ Institute for Child Health (ICH) statistical support team. 100 patients would suffice to be able to estimate agreement between methods, giving a 95% CI about $+/- (0.34 \times \text{standard deviation})$.

At GOSH approximately 1500 radiography-assisted procedures are performed on children annually. Of these it is estimated that about 1000 are performed on children between the ages of 8 months and 7 years old. Of these it is anticipated that about 750 would meet inclusion criteria without exclusion criteria, meaning that this study would be suitable for a single centre (GOSH).

Patient management and intervention

Patient management for general anaesthesia will continue according to usual paediatric anaesthetic standards. Anaesthesia will be induced by an intravenous or inhalational method. After administration of muscle relaxant, the patient will be intubated with a cuffed MicroCuff® endotracheal tube, which has been shown to be safe in children (19) and is even recommended by some experts as superior to an uncuffed endotracheal tube (20).

The size of the low-pressure, high-volume endotracheal tube shall be determined according to manufacturer's instructions (21). The anaesthetist will confirm the presence of an audible leak at <15 cmH₂O pressure as is typical in paediatric anaesthesia, and in the unlikely event that this does not exist then the endotracheal tube will be changed to one size smaller. Once a leak has been confirmed the cuff of the endotracheal tube will be inflated under guidance of a cuff manometer. The in-built ventilator's spirometric equipment will be used to measure expired tidal volumes and these will later be compared to set inspired volume to calculate the leak during cuff deflation.

An oesophageal and nasopharyngeal temperature probe will be inserted prior to commencement of the actual procedure (after anaesthesia has been established). The insertion depth of the nasopharyngeal probe will be estimated by a formula previously described (9):

$$\text{Length (cm)} = (\text{distance from tragus to nostril}) - 2$$

This length will then be adjusted at the discretion of the operator inserting the probe in order to achieve the level of the posterior border of the soft palate (position confirmed with laryngoscope).

The oesophageal probe will initially be inserted to a depth determined by a formula slightly adjusted from a previously described method to calculate the distance to the lower oesophageal sphincter in children (22):

$$\text{Length (cm)} = (0.226 \times \text{height}) + 5$$

Once the initial radiograph has been taken (timing of which shall be dictated by the surgical team as this radiograph will assist with the procedure), the intervertebral space between the 8th and 9th thoracic vertebrae will be identified and the distance between the end of the oesophageal probe and this landmark will be measured. The position of the end of the temperature probe will be adjusted to the level of T8/ T9, which corresponds to the lower third of the oesophagus.

The anaesthetic gas mixture flow will be set at 2L /min in order to standardize the flow of this potentially cooling factor between patients. The anaesthetist will set the ventilator mode to volume control ventilation (VCV) without leak compensation with a Peak End Expiratory Pressure (PEEP) of 5 and a tidal volume of 7 – 9 ml/kg. The inspiratory: expiratory (I:E) ratio will be set to 1:2. Approximately 1 minute following satisfactory positioning of the temperature probe, the temperature of the oesophageal and nasopharyngeal probes will be recorded over a period of 20 breath cycles (approximately 1 minute), while the ventilator's

spirometric equipment will be utilized to measure expired tidal volume and peak airway pressure..

The endotracheal tube cuff will now be deflated to allow an anaesthetic gas leak, thus simulating the use of an uncuffed endotracheal tube. The volume of air in the cuff will be adjusted by the anaesthetist to achieve a clinically soft audible leak (whilst on the ventilator). Temperature and spirometry measurements will recommence approximately 1 minute hereafter (simulating an uncuffed endotracheal tube scenario), again over a period of 20 breath cycles. Once this is completed the anaesthetist will use their discretion whether or not they wish to fully re-inflate (with cuff manometry) the endotracheal tube cuff or not for the remainder of the procedure.

As is usual during anaesthesia, standard body warming measures (aiming for normothermia) will be taken, guided by the measured temperatures.

Data collection

The following data will be collected:

Demographics – including date of procedure, date of birth, age, height, ASA status

Initial distance that oesophageal probe is inserted, based on formula described above

Distance of oesophageal probe tip away from T8/T9 intervertebral space

Temperature of nasopharyngeal probe at a point approximately 1 minute after satisfactory positioning at T8/T9 level and again 1 minute after cuff deflation to a clinically soft audible leak

During the periods of cuff inflation as well as cuff deflation, inspired and expired tidal volumes will be measured by spirometry over a 20 breath cycle, and these will later be used to calculate Fractional volume loss (FVL).

Ventilator settings including I:E ratio, PEEP, Peak AirWay Pressure (PAWP)

Distance of nasopharyngeal probe insertion

Complications of nasopharyngeal probe insertion (bleeding, failure)

Complications of oesophageal probe insertion (failure)

Cuff pressure utilized

Duration of study

It is estimated that about 1000 radiography-assisted procedures are performed annually on children between the ages of 8 months and 7 years old at GOSH. Of these, it is anticipated that about 750 would meet inclusion criteria without exclusion criteria. If a parental consent rate of 50% is achieved, then the study would estimate to run for 6 months (allowing for 40% of patients missed due to researcher unavailability) in order to recruit 100 patients.

Risks of study

Recruitment of patients will include only those who would anyway have received an endotracheal tube for anaesthesia (as opposed to an alternative anaesthetic airway such as a supraglottic airway device). The study population will be those children undergoing a procedure that requires radiography (e.g line insertion) ie there is a need for X-rays for surgical reasons. These X-rays will simultaneously be used to confirm optimal oesophageal probe position, and no radiation risk will be added for probe X-ray. Position will initially have been estimated with a formula and adjusted according to radiograph.

It is usual in anaesthesia to measure temperature intraoperatively, and common practice is to use a nasopharyngeal (23) or oesophageal probe when anaesthesia is expected to last longer than 30 minutes (24). As nasopharyngeal and oesophageal temperature probes are commonly inserted during general anaesthesia (25-27), practice will be little changed from standard during this study. Children will be recruited if they are expected to undergo anaesthesia for greater than 30 minutes. Insertion of an oesophageal temperature probe as well as a nasopharyngeal probe is expected to add only 1 minute to total anaesthetic time, meaning that the child will be kept asleep only fractionally longer than would otherwise have been the case if they were not recruited into the study. This short prolongation of anaesthesia will not have any significant clinical effects.

The insertion of a nasopharyngeal temperature probe can cause nasal bleeding (28) but this is self-limiting in the overwhelming majority of cases. Those with a known coagulopathy will not be recruited into this study due to risk of nasal bleeding. Failure to insert a nasopharyngeal probe can occasionally occur, for example due to previous nasal trauma, in which case success in the other nare is usually possible. Very rarely will a nasopharyngeal probe be unable to be inserted in both nares, in which case recruitment of the patient into the study will be abandoned. There is a possibility that the nasopharyngeal probe will be placed too deep, reaching the mouth. In this case, there is a possibility that ambient temperature may reduce the recorded temperature, causing inaccuracy. This risk will be minimized by the insertion of the temperature probe being done by the researchers, aiming to insert the probe's end to the level of the posterior border of the soft palate (under laryngoscopic view after estimating depth required by formula). Very rarely have other complications occurred with nasopharyngeal probes, including one case report relating to too deep insertion of nasopharyngeal probe during surgery on the oesophagus (29) and a report on defective nasopharyngeal probes (30), both scenarios of which are highly unlikely to be relevant in our proposed study.

The insertion of the oesophageal probe is a safe procedure, with very few side-effects reported in the literature. Rarely has an oesophageal temperature probe been inadvertently inserted intratracheally (31). If this were to occur, early diagnosis would be possible due to accompanying radiography, noting the probe to cross the carina. Rarely will oesophageal probe insertion fail, in which case recruitment into the study will terminate.

Statistics and data analysis

We consider a clinically unacceptable difference as a difference of greater than 0.5°C between methods.

The study recruitment rate will be assessed by recording patients successfully entered into the study as well as those for whom parental consent was not achieved. Demographic data will be appropriately recorded and analysed in terms of means and medians. Temperature measurements with the oesophageal probe will be compared to temperature measurements with the nasopharyngeal probe and mean differences, standard deviations, and 95% confidence intervals will be calculated and tabulated. Bland-Altman plots of the esophageal-nasopharyngeal temperature differences will be drawn. Differences will be checked for normality. Differences against mean will also be checked for variability (making sure that differences do not increase with mean). Linear regression analysis shall be utilized with scatter plot diagrams and r values calculated. A paired t-test will be performed to exclude systematic bias. Endotracheal leak, as measured by spirometry and fractional volume loss, will be measured, analysed and tabulated for means and standard deviations. It is anticipated that a clinically audible leak will correspond to a FVL of approximately 12.4 – 29.3% (based on data received directly from study author regarding IQR from a previous study (32)) for 50% of patients.

After the study has been completed we also plan to do a subgroup analysis for agreement between methods on 2 subgroups of patients: (1) those with FVL < 21.1% (2) those with FVL > 21.1%. This is in order to determine if there is any potential effect of leak size that might affect temperature differences.

Data handling

After parental written consent on recruitment, a data form with study number will be used (no hospital number or name of patient). Once completed, these patient data forms will be securely stored in a filing cabinet in the Anaesthetic office (access to which is controlled by GOSH swipe card). Each form will also be scanned and stored into a password-protected folder on the GOSH intranet “i drive”. Patient confidentiality will be ensured at all stages.

Study finances & disclosures

In order to meet the costs of consumables that would not routinely otherwise have been used in normal clinical management:

For oesophageal temperature probes: 100 probes would cost £330.70

For MicroCuff® endotracheal tubes: 100 tubes would cost £600

The cost for uncuffed Portex tubes that would otherwise have been used anyway is £123

We expect a possible extra 10% of consumables to be used for patients that might be recruited into the trial but are unable to complete the trial.

Total required = $(110\% \times £993.70) - £123 \approx £900$

Further savings will also occur due to minimal use of sevoflurane.

Discussions have taken place within the anaesthetic department (via the clinical lead in anaesthesia [name]) and funding has been internally arranged.

No authors shall be remunerated for their efforts and no conflicts of interest are declared.

Representatives from Covidien and Philips assisted in education of study authors regarding recording and retrieving temperature data

Publication plan

Following the study, the findings will be submitted to journal editors for consideration for publication in a peer-reviewed journal. Failing that, submissions will be made to conference or congress organisers with a view to present the findings in poster or oral presentation format. Raw data will be safely stored so that any potential future investigators can have access to this.

References

1. Torossian A. Thermal management during anaesthesia and thermoregulation standards for the prevention of inadvertent perioperative hypothermia. *Best practice & research Clinical anaesthesiology*. 2008;22(4):659-68.
2. Sessler DI. Complications and treatment of mild hypothermia. *Anesthesiology*. 2001;95(2):531-43.
3. National Institute for Health and Clinical Excellence. The management of inadvertent perioperative hypothermia in adults: full guideline [15 January, 2014]. 2008:[Available from: <http://www.nice.org.uk/nicemedia/live/11962/40429/40429.pdf>].

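### Does leaving the denominator of fractional volume loss unsettled (set or measured inspired volume) undermine the 21.1% leak split?

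*Combined protocol and SAP*

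**What the plan says.** Three sections bear on how leak is measured.

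- **Patient management and intervention**, on intubation: the ventilator's spirometer measures expired tidal volumes, and "these will later be compared to set inspired volume to calculate the leak during cuff deflation". This sentence speaks of the leak and does not name FVL.
- **Patient management and intervention**, on the recording period: the "spirometric equipment will be utilized to measure expired tidal volume and peak airway pressure". Measured inspired volume is not mentioned here. The ventilator is set to "volume control ventilation (VCV) without leak compensation with a Peak End Expiratory Pressure (PEEP) of 5 and a tidal volume of 7 – 9 ml/kg".
- **Data collection**: with the cuff inflated and again with it deflated, "inspired and expired tidal volumes will be measured by spirometry over a 20 breath cycle", and FVL is then calculated from these volumes.
- **Statistics and data analysis**: "Endotracheal leak, as measured by spirometry and fractional volume loss, will be measured, analysed and tabulated for means and standard deviations". The authors expect that "a clinically audible leak will correspond to a FVL of approximately 12.4 – 29.3" per cent in half of the patients, from an earlier study's interquartile range. A subgroup analysis of agreement then separates children below and above an FVL of 21.1%.

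No section writes out an FVL formula, says how the cuff-inflated reading enters it, or explains where 21.1% comes from.

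**The concern.** One description divides by a ventilator setting and the other by a measurement. If the ventilator delivers a volume different from the one set, the same child has two FVL values. Dividing by set volume would count a shortfall in delivery as leak. The mean FVL would move, and a fixed cut at 21.1% would fall at a different place on the measured-volume scale.

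The split at 21.1% is the only planned analysis that relates the size of the leak to the temperature difference, and cooling by escaped gas is the question raised in the Background. A cut given to one decimal place, on a quantity with no written formula, therefore looks exposed. The bedside text adds to the worry: someone following it alone might record expired volume and omit the inspired volume that Data collection requires.

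**Working it through.** **The plan's own precision figure.** The section on number of patients gives a 95% CI of about ±0.34 SD with 100 patients. This is the usual approximation for the interval around a Bland-Altman limit of agreement: 1.96 × √(3/100) = 0.339. It reproduces, and FVL does not enter it.

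**What links the two definitions.** Let S be set inspired volume, I measured inspired volume, E expired volume and r = I/S.

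- Measured-volume FVL: F = 1 − E/I
- Set-volume FVL: 1 − E/S = 1 − r(1 − F)
- Measured-volume FVL at which the set-volume version reads 21.1%: 1 − 0.789/r

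The definitions coincide at r = 1. The documents give no value or range for r, so 0.90 to 1.10 is an assumption, taken as the same for every child.

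**Shape of FVL.** Only the range 12.4 to 29.3% for half the patients is stated. Assume a normal shape with mean (12.4 + 29.3)/2 = 20.85% and SD (29.3 − 12.4)/(2 × 0.6745) = 12.5%. The mean shift is then (100 − 20.85)(1 − r) = 79.15(1 − r) points.

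| r (assumed) | Measured-volume FVL that reads 21.1% on set volume | Children changing subgroup | Shift in mean FVL (points) |
|---|---|---|---|
| 0.90 | 12.3% | 26.0% | +7.9 |
| 0.95 | 16.9% | 13.0% | +4.0 |
| 0.98 | 19.5% | 5.1% | +1.6 |
| 1.00 | 21.1% | 0 | 0 |
| 1.02 | 22.6% | 4.9% | −1.6 |
| 1.05 | 24.9% | 11.8% | −4.0 |
| 1.10 | 28.3% | 21.5% | −7.9 |

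Example: at r = 0.95 the boundary is 1 − 0.789/0.95 = 16.9%, and 13.0% of the assumed distribution lies between 16.9% and 21.1%.

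**What a common r leaves intact.** Set-volume FVL is then a straight-line, increasing function of measured-volume FVL. The children keep their order, and the correlation between the two versions is 1. The groups remain lower leak and higher leak, with the boundary moved.

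**Which text governs.** FVL is named together with its calculation in one place only, Data collection, and there both volumes are measured. The earlier sentence on set volume describes leak in general terms. It also sits beside a volume-controlled mode with leak compensation switched off, so the ventilator is not meant to add volume to offset the leak. That makes set volume an understandable shorthand for inspired volume, though it does not prove the two equal.

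**The case for a change.** The best case for a change is this. The sections disagree, and the bedside text fits the set-volume version better than the measured one. Choosing a denominator after seeing the data leaves some analytic freedom. The error also need not be uniform: if r averages 1 but varies between children with an SD of 3%, 5% or 10% (again assumed), simulation under a normal shape centred on 21.1% gives correlations between the two versions of 0.98, 0.95 and 0.84, with about 6%, 10% and 18% of children changing subgroup. Aligning the text would cost a sentence.

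The disagreement in wording stands, and tidying it would do no harm. The rest carries less weight. Data collection lists what must be recorded, and inspired volume in both cuff states is on that list, so the reading is planned. The freedom of choice is narrow, because that section already ties FVL to measured volumes.

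Nor can a gain be shown from fixing the denominator. The 21.1% cut and the 12.4 to 29.3% range come without a stated denominator. If the earlier study used set volume, insisting on measured volume would create a mismatch with it.

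Correcting each child's FVL by the cuff-inflated reading is no clear improvement either. It adds noise and removes any real leak past the inflated cuff: a residual leak of 2% or 5% would turn 21.1% into 1 − 0.789/0.98 = 19.5% or 1 − 0.789/0.95 = 16.9%. It may also be less comparable with the borrowed range.

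**Conclusion.** No change to the plan is needed. This is loose wording that an analyst resolves sensibly by following the one section that says how FVL is calculated: one minus expired over inspired volume, both measured, with the cuff deflated, over the 20 breaths.

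The possible effect runs from nil when delivered equals set volume to about a quarter of children changing subgroup at a 10% shortfall. Every figure other than nil rests on a departure that the documents do not report and on an assumed shape for FVL. Even then it reaches only descriptive leak summaries and one secondary split whose cut has no stated derivation. The temperature comparison, the 0.5°C criterion and the precision claimed for 100 patients do not depend on it.

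### Both probes are read in each child with the cuff inflated and then deflated, but no within-child comparison of the two cuff states is planned, so the cooling question in the Background is not directly analysed

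*Combined protocol and SAP*

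**What the plan says.** The title concerns "Correlation of nasopharyngeal and lower oesophageal temperatures in children ventilated with an endotracheal tube with leak", and Study objectives asks for agreement between the two sites in "children undergoing general anaesthesia with an endotracheal tube that has a leak". The Background ends on a different, explanatory question: "whether or not nasopharyngeal temperature is influenced by the cooling effects of these escaped gases or not".

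Patient management and intervention sets up two conditions in the same child. With the cuff inflated, "the temperature of the oesophageal and nasopharyngeal probes will be recorded over a period of 20 breath cycles"; this begins "Approximately 1 minute following satisfactory positioning of the temperature probe". The cuff is then let down to a soft audible leak to mimic an uncuffed tube, and temperature and spirometry are measured again about a minute later, over another 20 breaths. Spirometry is taken in both states, and expired volumes are compared with the set volume "to calculate the leak during cuff deflation".

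Statistics and data analysis then states that "Temperature measurements with the oesophageal probe will be compared to temperature measurements with the nasopharyngeal probe". Mean differences, SDs, 95% CIs, Bland-Altman plots, regression and a paired t-test for systematic bias follow. All of these read as probe against probe, and cuff state is not mentioned. FVL is to be summarised by mean and SD. Agreement is to be examined separately in patients with FVL below and above 21.1%, with the declared aim of looking for an effect of leak size. A difference above 0.5°C between methods is taken as clinically unacceptable.

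**The concern.** The design contains the contrast that bears most directly on the Background question: the same child, minutes apart, with and without a leak. The analysis section does not use it, and the inflated temperatures have no stated purpose.

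The FVL split does not take its place. On the natural reading it uses FVL with the cuff deflated, so both groups have an audible leak and the lower group is a smaller-leak group. If any audible leak cooled the nasopharynx by a similar amount, both groups would shift alike and their contrast would be near zero. A null split could then be misread as showing that leak does not matter.

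Tabulating the two cuff states side by side would show both mean differences. It would not give a confidence interval for the change, because that needs the SD of the paired changes.

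**Working it through.** **Inputs from the protocol.** n = 100, 95% confidence and a half-width of 0.34 SD (Feasibility of study/ number of patients); the 0.5°C limit and the 21.1% FVL cut (Statistics and data analysis); two readings per child in fixed order (Patient management and intervention).

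**Assumptions, not in the protocol.** The SD of the oesophageal minus nasopharyngeal difference is the same in both cuff states. The correlation between states, rho, is shown at 0, 0.5 and 0.9. The FVL cut divides the children 50/50, with 30/70 as an alternative.

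**1. The plan's own figure.** The CI half-width for a limit of agreement is 1.96 × SD × sqrt(3/n). At n = 100 this is 1.96 × sqrt(0.03) = 0.339 SD, which reproduces the stated 0.34. The figure fits one pair per child and does not show which cuff state is meant. Pooling both states as 200 independent pairs would give 1.96 × sqrt(3/200) = 0.240 SD. That is falsely narrow and is not the planned figure.

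**2. The FVL split.** The half-width for the difference in mean bias between subgroups is 1.96 × SD × sqrt(1/n1 + 1/n2).
- 50/50: 1.96 × sqrt(0.04) = 0.392 SD
- 30/70: 0.428 SD

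**3. The within-child change.** Its SD is SD × sqrt(2(1 − rho)), so the half-width is 1.96 × SD × sqrt(2(1 − rho)/100).

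| rho | SD of change | 95% CI half-width |
|---|---|---|
| 0 | 1.41 SD | 0.277 SD |
| 0.5 | 1.00 SD | 0.196 SD |
| 0.9 | 0.45 SD | 0.088 SD |

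For any rho of 0 or above this is tighter than the split, and it is measured against the inflated-cuff state.

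**4. In °C.** The largest SD that keeps 1.96 SD within 0.5°C at zero bias is 0.5/1.96 = 0.255°C. At that SD the change has a half-width of 0.071, 0.050 and 0.022°C for rho 0, 0.5 and 0.9; the even split has 0.100°C. At rho 0.5, an SD of 0.15 gives 0.029°C and an SD of 0.40 gives 0.078°C.

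**5. What drift could do.** Suppose the leak has no effect but the probe difference drifts by 0.2 SD between readings (0.2 × 0.255 = 0.051°C). The standard error of the mean change is 0.141, 0.100 and 0.045 SD, so the drift amounts to 1.41, 2.00 and 4.47 standard errors. In simulation the paired test was then significant in 28%, 51% and 99% of trials. A drift of 0.1 SD gave 10%, 16% and 60%. The precision that makes the contrast attractive also makes it sensitive to small artefacts.

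**The case against.** The strongest reply is that no stated objective is harmed. The purpose, the objective and the design label all speak of agreement; the cooling question is posed in the Background and is not listed as an objective. A clinician deciding whether to trust a nasopharyngeal probe when there is a leak needs the bias and limits of agreement with the leak present. Any cooling that matters shows there, whatever its cause. This stands, and it limits the point to an explanatory secondary analysis. A reader might infer from the gap that the study cannot answer its question. The documents do not support that, because title, objective and procedure all point to the deflated readings, which suffice for agreement.

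A reader might also infer that the FVL split is defective. It is not: it was declared as a leak-size analysis. That it cannot detect an effect identical at every leak size is true by construction.

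The third reply is that the within-child change is confounded. Order is always inflated then deflated, warming is active and guided by the measured temperatures, and the oesophageal probe has been positioned only about a minute before the first reading. This also stands. It calls for a stated caveat but does not justify leaving the inflated readings unanalysed.

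**Conclusion.** The point holds as a low-cost improvement. Two readings per child are taken in opposite leak conditions, no comparison between them is planned, and the FVL split has no no-leak reference, so the Background question is reached only indirectly. The agreement objective and the sample size of 100 are unaffected.

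The gain is an estimate of the change with its own interval: 0.28 to 0.09 SD for rho from 0 to 0.9, or 0.07 to 0.02°C at an SD of 0.255°C. Both are small against the 0.5°C limit. These sizes rest on equal SDs, an assumed rho and an assumed SD, none of which the protocol gives; the structural gap rests on none of them.

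It would be tempting to say that the paired change would prove or rule out cooling by the leak. The design does not support that: a drift of about 0.05°C could by itself give a significant result.

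**What to change.** Add to Statistics and data analysis, as a secondary analysis:

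- the within-child change in (oesophageal minus nasopharyngeal) from cuff inflated to cuff deflated, with mean, SD and 95% CI in °C, read against the 0.5°C limit and not by significance alone;
- FVL in both cuff states, so that the reader can see how close the inflated state is to no leak;
- a statement of limits: fixed order, active warming, recent repositioning of the oesophageal probe, and hence possible drift, so that the result supports a leak effect without isolating it.

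Keep the FVL split as the leak-size analysis.

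For clarification only:

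- state that the deflated readings, one pair per child, feed the main agreement analysis, and that inflated readings are reported separately and not pooled with them;
- give one rule for summarising each 20-breath recording. Data collection lists temperature at a single point, which may mean the start of that window, but the text should say so;
- add oesophageal temperature to the Data collection list, which at present names only the nasopharyngeal one.

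The cost is a few lines of analysis text and one line in the data list. No extra patients, measurements or procedures are needed.
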